### **Statistical analysis:**

The SPSS computer software (IBM SPSS Statistics v21.0; IBM Corp., USA) was utilized for the statistical analysis of the collected data in this study. The significance of the conducted statistical results was considered at two tailed  $\alpha$  of .05. Normal distribution of the data was tested utilizing the Shapiro-Wilk test and the skewness test considering skewness z-score threshold values range from -3.29 to +3.29. All the continuous variables were not normally distributed, except for age and OHIP scores before treatment. Descriptive statistics for normally distributed continuous variables (age and OHIP scores before treatment) included the mean, standard error, standard deviation, median, maximum value, minimum value, and confidence intervals. Meanwhile, descriptive statistics for the non-normally distributed continuous variables included the mean, standard deviation, median, interquartile range, minimum value, and maximum value. Categorical variables in this study (presence of redness, erosion, keratosis, ulceration, and denture fissuratum) were presented as frequencies and percentages.

The Wilcoxon Signed Ranks test was used to test paired differences in satisfaction ratings, dentist's evaluations, and OHIP-EDENT scores after using carved and non-carved lower dentures. The Mann Whitney U test was utilized to identify differences in satisfaction ratings, dentist's evaluations, and OHIP-EDENT scores between genders. Spearman's Rho rank correlations were used to identify the correlations between satisfaction ratings, dentist's evaluations, and OHIP-EDENT scores. Associations between identification of lesions following denture use (presence of redness, erosion, keratosis, ulceration, and denture fissuratum) and having the retromolar pad area of the lower denture carved or not were tested via Fisher's Exact test.

The multiple linear regression analysis was used to identify the contribution of having the retromolar pad area carved or not, satisfaction ratings, and dentist evaluation towards the prediction of OHIP-EDENT scores considering the confounding effects of gender and age.

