## Results

The data was collected from a total of 49 participants (23 females and 27 males), and was then processed and analyzed. Participants age ranged from 40 to 78 years old (mean age= 62.8 years old, SD= 8.01, SE= 1.145, median= 63.0, 95% CI= 60.51 – 65.12).

Table 1 demonstrates the descriptive statistics for continuous variables in this study including dentist evaluations of dentures, patients' satisfaction with dentures, and OHIP-EDENT scores among the participants of this study. Paired comparisons of carved and non-carved lower dentures showed that patient satisfaction with retention at function ( $P= .002$ ) and comfort during the use of carved lower dentures ( $P= .026$ ) were significantly higher than non-carved lower dentures (Table 1). Furthermore, the patients demonstrated a tendency to be more satisfied with denture retention at rest as well as during eating when used carved lower dentures in comparison to non-carved ones. This difference was not significant but was close to be significant ( $P= .052$ ,

Table 1). In addition, carved lower dentures were associated with lower OHIP scores (better impacts on oral health) than the non-carved lower dentures; however, the difference was not significant ( $P= .055$ , Table 1). Nevertheless, this tendency was confirmed by the Mann Whitney U test as a significant difference was found in the OHIP scores between carved and non-carved lower dentures ( $MWU= 887.0$ ,  $Z= -2.241$ ,  $P= .025$ ). The carved lower dentures were associated with lower OHIP scores indicating better impacts on oral health than the non-carved dentures.

Table 2 presents the distribution (frequencies and percentages) of redness, erosion, keratosis, ulceration, and denture fissuratum following the use of the tested complete denture designs during this study. Redness was the most observed mucosal change, 18.4% with non-carved dentures and 12.2% with carved dentures. No significant differences in mucosal changes were observed between carved and non-carved lower dentures ( $P> .05$ , Table 2).

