Table 5 presents correlations between age, patient satisfaction, and OHIP scores. The results show that older patients were more comfortable with upper dentures than younger patients (Spearman Rho= 0.309,  $P= .031$ , Table 5). Also, higher pain scores were associated with higher OHIP scores (i.e. worse impacts) after using carved ( $P= .001$ ) and non-carved ( $P< .001$ ) lower dentures (Table 5). In addition, lower OHIP scores (i.e. better impacts) were associated with higher satisfaction with retention at rest, retention at function, denture comfort, general satisfaction with dentures, retention during eating, and retention during speaking after using carved or non-carved lower dentures ( $P< .05$ , Table 5). Besides, correlations between age and dentist rating of dentures showed that older participants were found to have better dentist ratings of retention (Sperman Rho= 0.402,  $P= .004$ ) and higher stability (Spearman Rho= 0.402,  $P= .003$ ) of upper dentures than younger participants.

A multiple linear regression analysis was used to identify the contribution of having the retromolar pad area carved or not, satisfaction ratings, and dentist evaluation of dentures towards the prediction of OHIP scores considering the confounding effects of gender and age (Table 6). Being a female, having lower dentist ratings of denture esthetics, and having more pain due to lower dentures were associated with higher scores of OHIP indicating worse oral health impacts

of the prosthesis ( $P < .05$ , Table 6). Being a female was associated with an increase of OHIP scores by 4 units ( $P = .007$ ). Also, for each decreased unit of dentist ratings of denture esthetics, the OHIP scores were increased by 2 units ( $P = .018$ ). Furthermore, for each increased unit of pain levels due to lower dentures, the OHIP scores were increased by 0.7 units ( $P = .020$ ) (Table 6).

Further multiple linear regression analyses were conducted to identify the contribution of having the retromolar pad area carved or not and dentist evaluation of dentures towards the prediction of patient satisfaction with different denture aspects considering the confounding effects of gender and age (Table 7). The results showed that carved lower dentures were associated with 1.144 times higher satisfaction with lower denture retention during function ( $P = .040$ , Table 7). **[name] please note that Being carved or not was significant predictor for retention of the denture during function.**

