Besides, patients satisfaction with lower denture retention at rest was decreased by 0.053 unit for each year increase in the age ( $P = .027$ , Table 7). Also, being a female was associated with higher patient satisfaction with lower denture retention at rest ( $B = 0.970$ ,  $P = .033$ ), lower denture retention at function ( $B = 1.404$ ,  $P = .027$ ), lower denture comfort ( $B = 1.374$ ,  $P = .007$ ), general satisfaction with upper and lower dentures ( $B = 1.361$ ,  $P = .002$ ), and retention of upper and lower dentures during eating ( $B = 0.978$ ,  $P = .036$ ) (Table 7).

In addition, higher levels of perceived pain due to lower dentures were associated with lower levels of satisfaction with lower denture retention at rest ( $B = -0.184$ ,  $P = .032$ ), lower denture retention at function ( $B = -0.365$ ,  $P = .002$ ), lower denture comfort ( $B = -0.440$ ,  $P < .001$ ), general satisfaction with upper and lower dentures ( $B = -0.254$ ,  $P = .002$ ), retention of upper and lower dentures during eating ( $B = -0.320$ ,  $P < .001$ ), and retention of upper and lower dentures during

speaking ( $B = -0.235$ ,  $P = .005$ ) (Table 7). Furthermore, higher dentist ratings of lower denture stability (**[name] please note for the discussion that this could be explained by that stability is related to each of retention, support and occlusion**) was associated with higher patient satisfaction with lower denture retention at rest ( $B = 0.527$ ,  $P = .037$ ), lower denture retention at function ( $B = 0.958$ ,  $P = .005$ ), and lower denture comfort ( $B = 0.723$ ,  $P = .011$ ) (Table 7).

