General satisfaction with upper and carved lower dentures	Rho	.058	-.316	-.491
	P	.695	.027	<.001
Retention during eating with upper and non carved lower dentures	Rho	.260	-.582	-.032
	P	.072	<.001	.828
Retention during eating with upper and carved lower dentures	Rho	-.069	-.320	-.459
	P	.639	.025	.001
Smile and appearance of upper and	Rho	-.102	-.290	-.196

non carved lower dentures	P	.484	.043	.177
Smile and appearance of upper and carved lower dentures	Rho	.181	-.359	-.207
	P	.213	.011	.153
Retention during speaking with upper and non carved lower dentures	Rho	.066	-.435	-.145
	P	.655	.002	.321
Retention during speaking with upper and carved lower dentures	Rho	-.016	-.276	-.505
	P	.911	.055	<.001
OHIP score before treatment	Rho	-.104	.253	-.052
	P	.479	.079	.722

NCLD= Non-carved lower denture, CLD= Carved lower denture, OHIP= Oral Health Impact Profile – 14, Rho= Spearman correlation coefficient, P= Two tailed probability value.

**Table 6.** Linear regression analyses to predict OHIP scores after treatment utilizing the demographic variables, having the lower denture carved or not, dentist ratings of lower dentures, and patient satisfaction with dentures among the study sample (n= 50).

Dependent variable	Predictors*	Unst Co		St Co	t	P	95% CI for B	
		B	SE	Beta			Lower Bound	Upper Bound
OHIP scores after treatment R  = .468 DW = 1.837	Constant	63.274	13.648	---	4.636	<.001	36.118	90.430
	Gender	4.063	1.465	.281	2.774	.007	1.149	6.977
	Age	-.132	.080	-.146	-1.645	.104	-.292	.028
	Carved denture or not	-1.324	1.222	-.092	-1.084	.282	-3.755	1.107
	Dentist rated lower denture retention	.314	.507	.084	.619	.538	-.695	1.323
	Dentist rated lower denture stability	-.704	.793	-.151	-.888	.377	-2.282	.873
	Dentist rated lower denture support	.477	.833	.069	.572	.569	-1.182	2.135
	Dentist rated lower denture esthetics	-2.070	.860	-.245	-2.408	.018	-3.780	-.359
	Perceived pain due to lower denture	.711	.299	.253	2.374	.020	.115	1.306
	Patient satisfaction with lower denture retention at rest	-.213	.473	-.064	-.451	.653	-1.154	.727
	Patient satisfaction with lower denture retention at function	-.281	.400	-.115	-.704	.484	-1.077	.514
	Patient satisfaction with lower denture Comfort	.090	.522	.033	.173	.863	-.948	1.128
	Patient satisfaction with easiness of lower denture insertion	-.359	.473	-.068	-.758	.450	-1.300	.583
	Patient general satisfaction with upper and lower dentures	-.244	.518	-.066	-.471	.639	-1.275	.787

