	Patient satisfaction with retention of upper and lower dentures during eating	-.207	.504	-.061	-.411	.682	-1.211	.796
	Patient satisfaction with smile and appearance of upper and lower dentures	-1.720	.888	-.188	-1.937	.056	-3.488	.047
	Patient satisfaction with retention of upper and lower dentures during speaking	-.653	.366	-.177	-1.787	.078	-1.381	.074

R^2= Coefficient of determination, DW= Durbin Watson statistic, Unst Co= Unstandardized coefficient, St Co= Standardized coefficient, B= Beta statistics, SE= Standard Error, t= t statistics, P= Two tailed probability value, CI= Confidence intervals. \*Gender, age, having the lower denture carved or not, and dentist ratings of lower dentures, and patient satisfaction with dentures were entered in the regression model.

**Table 7.** Linear regression analyses to predict patient satisfaction with different denture aspects utilizing the demographic variables, having the lower denture carved or not, and dentist ratings of lower dentures among the study sample (n= 50).

Dependent variable	Predictors*	Unst Co		St Co	t	P	95% CI for B	
		B	SE	Beta			Lower Bound	Upper Bound
Patient satisfaction with lower denture retention at rest R  = .295 DW=2.000	Constant	6.768	3.155	---	2.145	.035	.499	13.038
	Gender	.970	.449	.222	2.163	.033	.079	1.862
	Age	-.058	.026	-.211	-2.242	.027	-.109	-.007
	Carved denture or not	.338	.395	.078	.856	.394	-.447	1.124
	Dentist rated lower denture retention	-.170	.164	-.151	-1.035	.303	-.495	.156
	Dentist rated lower denture stability	.527	.249	.373	2.114	.037	.032	1.022
	Dentist rated lower denture support	.080	.264	.038	.301	.764	-.446	.605
	Dentist rated lower denture esthetics	-.021	.273	-.008	-.075	.940	-.564	.523
	Perceived pain due to lower denture	-.184	.084	-.216	-2.184	.032	-.351	-.017
Patient satisfaction with lower denture retention at function R  = .309 DW=1.728	Constant	4.512	4.410	---	1.023	.309	-4.249	13.273
	Gender	1.404	.624	.238	2.251	.027	.165	2.643
	Age	-.031	.036	-.084	-.864	.390	-.103	.041
	Carved denture or not	1.144	.549	.195	2.085	.040	.054	2.235
	Dentist rated lower denture retention	-.266	.229	-.175	-1.158	.250	-.722	.190
	Dentist rated lower denture stability	.958	.335	.504	2.858	.005	.292	1.623
	Dentist rated lower denture support	-.166	.371	-.059	-.446	.657	-.904	.572
	Dentist rated lower denture esthetics	-.431	.382	-.125	-1.128	.262	-1.189	.328

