	Dentist rated lower denture retention	-.166	.168	-.151	-.987	.326	-.499	.168
	Dentist rated lower denture stability	.101	.255	.074	.397	.693	-.406	.609
	Dentist rated lower denture support	.111	.271	.054	.410	.683	-.427	.650
	Dentist rated lower denture esthetics	-.209	.280	-.084	-.745	.458	-.766	.348
	Perceived pain due to lower denture	-.320	.086	-.386	-3.713	<.001	-.491	-.149

	denture							
Patient satisfaction with smile and appearance of upper and lower dentures R  = .092 DW=1.959	Constant	9.960	1.298	---	7.676	<.001	7.382	12.539
	Gender	.235	.184	.149	1.275	.206	-.131	.602
	Age	-.009	.011	-.091	-.856	.394	-.030	.012
	Carved denture or not	.014	.163	.009	.088	.930	-.309	.337
	Dentist rated lower denture retention	-.085	.067	-.209	-1.264	.210	-.219	.049
	Dentist rated lower denture stability	.078	.102	.153	.761	.449	-.126	.282
	Dentist rated lower denture support	-.112	.109	-.147	-1.027	.307	-.328	.104
	Dentist rated lower denture esthetics	.115	.112	.124	1.021	.310	-.109	.338
	Perceived pain due to lower denture	-.067	.035	-.219	-1.952	.054	-.136	.001
	Constant	12.767	3.044	---	4.194	<.001	6.718	18.816
Patient satisfaction with retention of upper and lower dentures during speaking R  = .185 DW=2.367	Gender	.702	.433	.179	1.623	.108	-.158	1.562
	Age	-.019	.025	-.076	-.754	.453	-.068	.031
	Carved denture or not	-.280	.381	-.072	-.735	.464	-1.038	.477
	Dentist rated lower denture retention	-.009	.158	-.009	-.055	.957	-.323	.305
	Dentist rated lower denture stability	.254	.240	.201	1.056	.294	-.224	.731
	Dentist rated lower denture support	-.074	.255	-.039	-.290	.773	-.581	.433
	Dentist rated lower denture esthetics	-.462	.264	-.202	-1.752	.083	-.986	.062
	Perceived pain due to lower denture	-.235	.081	-.309	-2.903	.005	-.397	-.074
	Constant	12.767	3.044	---	4.194	<.001	6.718	18.816
	Gender	.702	.433	.179	1.623	.108	-.158	1.562

R^2= Coefficient of determination, DW= Durbin Watson statistic, Unst Co= Unstandardized coefficient, St Co= Standardized coefficient, B= Beta statistics, SE= Standard Error, t= t statistics, P= Two tailed probability value, CI= Confidence intervals. \*Gender, age, having the lower denture carved or not, and dentist ratings of lower dentures were entered in the regression model.

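### Tables 6 and 7 fit 98 paired crossover records as independent rows, and the retention-at-function block of Table 7 cannot come from a single model

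*SAP*

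**What the plan says.** The title describes a crossover trial. In Statistical analysis, the SAP compares carved and non-carved dentures with a paired test, the Wilcoxon signed ranks test. For the regression it says: "The multiple linear regression analysis was used to identify the contribution of having the retromolar pad area carved or not". Gender and age are introduced there as confounders. For the satisfaction outcomes of Table 7, Results adds: "Further multiple linear regression analyses were conducted to identify the contribution of having the retromolar pad area carved or not".

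The Table 6 caption describes a sample "having the lower denture carved or not, dentist ratings of lower dentures, and patient satisfaction with dentures among the study sample (n= 50"), and the Table 7 caption one "having the lower denture carved or not, and dentist ratings of lower dentures among the study sample (n= 50"). The footnotes list what went in. For Table 6: "having the lower denture carved or not, and dentist ratings of lower dentures, and patient satisfaction with dentures were entered in the regression model". For Table 7: "having the lower denture carved or not, and dentist ratings of lower dentures were entered in the regression model". Neither names a participant, period or sequence term. The Table 7 footnote does not mention pain, yet each of its eight models prints a pain row.

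Results then reports covariate findings, for example that "being a female was associated with higher patient satisfaction with lower denture retention at rest", and singles out carving as a predictor of satisfaction with retention during function, describing B = 1.144 as a multiple.

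**The concern.** Each participant contributes one record per denture design. Ordinary regression on the stacked records treats a person's two records as if they came from different people. A covariate that is constant within a person, such as gender or age, is then credited with more independent information than it has. A covariate that changes within a person, such as carving, loses the benefit of the pairing. With positive residual correlation, gender and age look too precise and carving not precise enough.

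The retention-at-function block is a second, separate problem. It carries the only significant carving coefficient in either table, and its rows do not agree with one another. If they come from two different fits, the reader cannot tell which model supports P = .040.

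**Working it through.** **1. Number of records.** Inputs: SE and 95% CI of each constant (Tables 6 and 7). Critical t = half-width / SE; residual df follows from t; records = df + predictors + 1.

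- Table 6: (90.430 − 36.118)/2 = 27.156; 27.156/13.648 = 1.98974. With three-decimal rounding only df = 81 fits. Records = 81 + 16 + 1 = 98.
- Table 7, seven models other than retention at function: for example, at rest (13.038 − 0.499)/2 = 6.2695; 6.2695/3.155 = 1.98716, so df 87–89. The range common to all seven is 88–89, and 89 + 8 + 1 = 98.
- With 50 independent rows, df would be 33 and 41, and critical t would be 2.035 and 2.020.

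**2. Number of participants.** Table 2 counts are 40 + 9 = 49 and 43 + 6 = 49. In Table 5, rho .309 with P .031, .269 with .061 and −.226 with .119 each fit n = 49 only. The Mann-Whitney test in Results, where "a significant difference was found in the OHIP scores between carved and non-carved lower dentures", agrees:

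- 49 v 49: (887 − 1200.5)/√(49² × 99/12) = −313.5/140.74 = −2.227 before ties.
- 50 v 50: −363/145.06 = −2.502.
- Printed: −2.241. A tie correction enlarges |Z|, so only 49 v 49 fits.

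Hence 49 × 2 = 98. Neither 81 nor 89 df leaves room for fixed participant terms.

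**3. Effect on gender and age.** Assumption: a person's two residuals correlate at rho. Approximation: corrected t = printed t/√(1 + rho), on 49 − 3 = 46 df (critical t 2.013). Threshold rho = (t/2.013)² − 1.

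| Result | t | Threshold rho | P at .1 / .2 / .3 / .5 |
|---|---|---|---|
| Gender, eating | 2.126 | .12 | .048 / .058 / .069 / .089 |
| Gender, at rest | 2.163 | .15 | .045 / .054 / .064 / .084 |
| Age, at rest | 2.242 | .24 | .038 / .046 / .055 / .074 |
| Gender, function | 2.251 | .25 | .037 / .046 / .054 / .073 |

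The last row is rough, given step 4. At rho .5, gender stays significant for comfort (.030), general satisfaction (.012) and OHIP (.028).

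**4. The retention-at-function block.**

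*SE ratios.* Models with the same rows and predictors must have SEs in constant ratio. Relative to the at-rest model, one factor fits each of the other six within rounding (comfort 1.1163–1.1170, for example). For function the ratios are gender 1.390, carving 1.390, retention 1.396, stability 1.345, support 1.405, esthetics 1.399 and pain 1.333. Rounding allows 1.387–1.392 for gender, 1.341–1.350 for stability and 1.401–1.410 for support, so no common factor exists.

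*Df.* (13.273 + 4.249)/2 = 8.761; 8.761/4.410 = 1.98662, so df 90–91. With seven predictors, 98 − 7 − 1 = 90.

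*Fit at the means.* Least squares evaluated at the predictor means returns the outcome mean. Inputs: averages of the paired Table 1 means, age 62.8, and (assumed) 1/2 coding of gender and carving with 22 women of 49. Without pain: 4.512 + 2.034 − 1.947 + 1.716 − 2.176 + 8.138 − 1.480 − 3.829 = 6.97. Adding pain, −.365 × 1.64 = −.599, gives 6.37. The outcome mean is (6.33 + 7.59)/2 = 6.96, and coefficient rounding allows about 0.05. The other seven models match their outcome means within about 0.04, and only with pain (at rest: 8.35 with, 8.65 without, observed 8.365).

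*Residual SD.* The pain row (t = −3.251) implies that adding pain scales the residual SD by √[(1/(1 + 3.251²/89)) × 90/89] = .951. Then 1.333/.951 = 1.402, close to the support and esthetics ratios.

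**5. Carving coefficient with pain included (rough).** SE: .395 × 1.335 (pain-row CI widths, .446/.334) = .527. B = 1.144 + .365δ, where δ is the adjusted carving difference in pain. Assuming δ from −.4 to −.88 (the raw difference, 1.20 − 2.08), B runs from 1.00 to .82 and P from about .06 to .12.

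**The case against.** **Different data.** A reader might infer that the retention-at-function model was fitted to different data, because 90–91 df with the eight printed predictors means 99 or 100 rows. The documents do not support that. Forty-nine participants give at most 98 records, and the df, the fit at the means and the residual SD all point to the same 98 records with pain left out.

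**The captions.** The n = 50 most naturally counts participants, and the 49-versus-50 conflict runs through the whole document. That is fair. The caption is not itself a regression error, but it gives neither the records analysed nor the 49 participants that Tables 2 and 5 imply.

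**The size of rho.** The loss of significance depends on an assumed rho, and all four results stay below .05 at rho .1. This stands. Treating the Wilcoxon Z roughly as t, Table 1 suggests raw within-person correlations near .49 at rest and .23 for eating, but these are not residual correlations. The Durbin-Watson values do not settle the matter either: they depend on row order, and if the file is stacked by design they carry no information about pairs.

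**The direction for carving.** Under positive rho, stacking is conservative for carving, so it did not create P = .040. This also stands. A refit that includes pain may weaken that coefficient, while allowing for pairing may sharpen it.

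**Conclusion.** The concern holds on two counts. First, Tables 6 and 7 treat 98 paired records as independent; the printed intervals establish this firmly, and nothing in the text names a participant term. The harm is confined to secondary results. Four gender and age findings may not survive a modest positive rho, and three gender findings are robust up to .5. It would go too far to say that any of them is lost, since rho is unknown.

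Second, the retention-at-function block is not one model. That it mixes a pain-free fit with a pain row from another fit is the explanation that best matches the figures; it rests on rounded values and on 1/2 coding. The P of .06 to .12 for carving is indicative only and leaves pairing out, so no corrected interval is claimed. The paired Wilcoxon comparisons of carved and non-carved dentures, including retention at function (P = .002), are unaffected.

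**What to change.** - Refit Table 6 and all eight Table 7 models with a participant random intercept, or with GEE or cluster-robust standard errors by participant. Add period and sequence where they were recorded.
- Use one stated predictor set for all eight Table 7 outcomes. Decide explicitly whether pain belongs in it: pain is itself rated after each denture, so adjusting for it changes what the carving coefficient means. Make the footnote match.
- Give participants and records separately in each caption.
- Restate the gender, age and carving results from the refit, and describe the carving coefficient as 1.144 rating points (or the refitted value), since B is a difference and not a ratio.

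The cost is a rerun on the same data with a different procedure. The downside is that some gender, age or carving results may lose significance.
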